4.0 Goals/Aims

4.1 Goals This project will apply a three-armed randomized block design to identify whether financial incentives are effective in increasing acceptance of, and engagement in, smoking intervention services as well as smoking cessation amongst Group Health Cooperative (GHC-SCW) patients who smoke. All members of the GHC-SCW Cigarette Users Registry (i.e., individuals who the health system believes are smokers, the 'Registry') at the time of implementation will be eligible to participate. Smokers who speak with the TCOS staff when called for standard care management outreach following a recent primary care visit or during an annual outreach call and listen to the description of smoking treatments will be randomized to receive one of three incentive amounts (\$0, \$100, & \$50) for continuing treatment planning, establishing a target quit date and completing two telephone counseling sessions. Participants will be told about the size of their incentive, which in theory will increase their likelihood of engaging in smoking treatment and therefore, quitting smoking successfully. For the non-\$0 incentive groups, ½ the total value will be apportioned for completion of each a Pre-quit

counseling call and a Week 4 counseling call. Participants (N=540) will be recruited in up to 6 primary care clinics with randomization blocked on clinic so that roughly 1/3 of all enrollees in a given clinic will be in each of the treatment use incentive conditions to avoid incentive by clinic confounds. Sex and minority status will also be used as blocking factors to limit confounding the impact of the incentive on these demographic characteristics.

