6.4 Consent & Enrollment

GHC-SCW TCOS staff will be responsible for program implementation and data documentation (using existing EHR and administrative data fields) except for 3- and 6-month Follow Up survey collection completed by the research staff. Only limited patient and systems data will be shared with the research team documenting which patients were called as standard practice but declined study participation.

All patients who agree to the study offer – tailored to their assigned Treatment Engagement Incentive value (Attachment B: Invite script), and pass the inclusion and exclusion criteria for Treatment Engagement Incentive study participation will be read an oral consent script by a healthcare system TCOS (see uploaded Recruitment Call script). The consent script read to participants over the phone conveys the key points regarding study procedures; risks; and participant rights, protections, and benefits, and does so in accessible language (assessed for reading level). The consent will inform patients that some monetary payments may be offered as part of the study for engaging in study components, including \$20 for completing a telephone survey 6 months after their original Target Quit Date and \$50 for those who report smoking abstinence at 6 months who complete an in-person breath CO breath test, urine, or saliva test, but the [incentive] amounts available will not be disclosed (so that some patients will not refuse further engagement due to disappointment with their incentive amount). Prospective participants will be given an opportunity to ask questions and raise concerns during this process, which will be addressed prior to seeking oral consent. Informed consent for study participation will be formally documented electronically in the UW-ICTR REDCap instance study database. Following enrollment for those who consent, TCOS staff will send out a letter in hard copy to the participant at the address provided (see uploaded Study Information Sheet). This letter will remind the participant of study procedures and will include a detailed study information enclosure containing all required elements of informed consent and HIPAA authorization.

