6.5 Randomization

Randomization will occur during the contact call immediately after patients have been told of their smoking treatment options. The TCOS will then use randomization tables developed by UW-CTRI to randomize potential enrollees, blocked by clinic, sex, and race, into 1 of 3 engagement incentive conditions (\$0, \$100, or \$50). After randomization, patients will be offered smoking treatment with the incentive for treatment entry (engagement) to which they had been randomized. This offer will require the participant to agree to set a stop-smoking quit date within the next 30 days. This offer will occur prior to the patient's provision of consent to participate in research. The patient must be offered the incentive up-front to see if this increases their treatment engagement (which necessarily includes agreement to it/consent); offering the incentive after agreeing to participate in treatment would not reveal the effects of the incentive on spurring engagement. Thus, we are interested in the effects of incentives on both agreement to enter treatment and actual likelihood of engaging in it. If a patient decides to accept the treatment offer, s/he will be consented and will set a target quit date with the TCOS (within 1 month of the contact phone call). For patients who are unwilling to set a stop-smoking quit date within the next 30 days the TCOS will describe all stop-smoking treatment options that are available as part of usual care and encourage the patient to call the TCOS back when ready to set a quit date within 30 days. For patients who decline the research study, the TCOS will describe all stop-smoking treatment options that are available as part of usual care and provide quit smoking treatment as usual.

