9.3 Planned Analysis

Primary Aim

- To determine the relations between treatment engagement financial incentive amounts offered and likelihood of patient engagement in smoking cessation treatment (defined as setting a TQD and completing the two phone counseling calls (Pre-quit + Week 4).

Primary analysis. The primary outcome measure will be patient engagement in smoking cessation treatment (defined as setting a TQD and the number of completed phone counseling contacts). We will determine the percentage of those in each incentive condition who engage in smoking cessation treatment. We will use logistic regression analyses to contrast the likelihood of engaging in any smoking treatment (vs none) for the three incentive conditions (0 incentive, \$100, and \$50), with the 0 incentive condition being the reference condition in the primary analysis. We will also examine incentive condition effects on the number of scheduled counseling visits completed (0-3 visits) via ordinal logistic regression.

Additional exploratory analyses related to the primary aim. In additional exploratory analyses, we will determine the percentage of all GHC patients who are contacted by the TCOS and offered the Treatment Engagement Incentive. We will separately determine the percentage of those in each incentive condition who agree to set a TQD. We will use logistic regression analyses to contrast the likelihood of engaging in smoking treatment for the three incentive conditions, with (as mentioned above) the 0 incentive condition being the reference condition in the primary analysis, followed by comparison of the \$100 and \$50 conditions both with the reference condition and with one another. The primary analyses will not use covariates. Follow-up analyses will use the patient's home clinic and the patient's TCOS as covariates. Furthermore, using logistic regression, we will examine the relation between incentive condition and use of pharmacotherapy as the outcome (with medication orders and pick-up entered in the EHR and/or billing data).

Exploratory Aims

- Conduct exploratory analyses on the effects of the different incentive engagement amounts on biochemically confirmed point-prevalence 6-month abstinence and determine whether incentive conditions affect abstinence via their effects on smoking treatment engagement (i.e., whether smoking treatment engagement mediates the relations between different engagement incentive conditions and 6-month smoking abstinence).

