Analysis. Logistic regression will be used to determine whether the different incentive levels (\$0, \$100, \$50) produce effects on 6-month, biochemically confirmed point prevalence smoking

abstinence using the strategy described for Primary Aim. Dummy coding will be used to compare: 1) each positive incentive condition with the 0 incentive condition, and 2) the two positive incentive conditions will be compared with one another. The primary analyses will not use covariates. Secondary models will adjust for the patient's home clinic and the patient's TCOS as covariates, Gender, race, cigarettes smoked/day will be added as covariates in later analyses. Mediational analyses will be done using incentive condition as the independent variable, engagement data as mediators (attendance at the initial treatment contact, number of counseling contacts made, or use of smoking medication). The outcome variable will be smoking abstinence at 3 months (self-report only) and 6 months (biochemically confirmed self-report).

- To determine the incremental cost-effectiveness of the different financial engagement incentive amounts with regard to total program costs vs. usual care, net monetary benefit (NMB), cost per quit, and incremental cost-effectiveness ratios (ICERs), with the last determined with regard to cost of additional smoker engaged in treatment and each additional individual who quits smoking.

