Analysis. Cost data will come from: healthcare system costs in terms of outreach communications, TCOS time (related to outreach and counseling efforts), implementation costs, incentive costs, and medication expenditures (including related physician screening when it occurs). We will use methods recommended by the US Panel on Cost-Effectiveness in Health and Medicine¹⁰ and consistent with our prior research. We will measure costs from a societal perspective using data on smoking cessation benefits from publicly available Medicare and Medicaid reimbursement rates. Cost estimates will be converted to a common year and QALYs will be computed, using a rate of 3% to discount future outcomes and costs to present value. We will also conduct probabilistic sensitivity analyses to account for uncertainty. We will determine net monetary benefit (NMB), cost per quit (using 6 month abstinence rates), and incremental cost-effectiveness ratios (ICERs)¹¹. The components of NMB will be the added costs of the various incentive levels and the monetized value of the QALYs added by the treatments. Total intervention and implementation costs (including outreach and added TCOS time for intervention, implementation, and incentives) will be compared to program costs of the usual care approach to tobacco use (the TCOS intervention program prior to the incentive study implementation).

- To determine the representativeness of smoking treatment reach and smoking abstinence outcomes generated by the various engagement incentive amounts with regard to different groups of smokers: e.g., those low in socio-economic status, priority populations, different racial and ethnic groups.

Analysis. We will extract data from the EHR to characterize the healthcare system population of patients who smoke with regard to such factors as: gender, race, ethnicity, insurance mix. Such person factors will be related to the likelihood that the patient: responds to TCOS outreach, agrees to accept smoking treatment (agrees to a TQD and completes a counseling call), completes up to 3 counseling calls, picks up smoking medications, and achieves long-term abstinence. Logistic regression will be used to examine the likelihood that different person factors are significantly related to the various outcomes under the different incentive levels.

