9.4 Power

This study is powered to detect a 12 percentage point difference in treatment engagement rates (defined as setting a TQD and completing 2 treatment phone counseling contacts) as a function of incentive amount. We believe that this rate is both feasible and of public health significance. We anticipate that the 0 incentive condition will have an engagement rate of about 15%. Since the rate of smoking treatment engagement is generally only about 5-7% in studies where incentives are not used we believe a 15% rate is conservative. We anticipate increased engagement in the control condition, relative to these earlier studies, because we believe it will be increased by TCOS contact and the opportunity to set a quit date on the contact call. We believe that a 12 percentage point increase above the 15% rate (to 27%) would be of public health significance. A total of 180 participants per group are needed to have power of .80 with alpha = .05 in a two-tailed test. This would translate into a study N = 540 with 180/condition for the comparison of each positive incentive condition vs the control condition. We make no a priori prediction about whether the \$100 incentive condition will increase engagement relative to the \$50 condition, but we certainly believe it will increase engagement relative to the 0 incentive condition. . Therefore, we propose an overall N=540.

While engagement is the principal outcome of this research we nevertheless have determined the effect size (increment in percent abstinent) we would need to have adequate power to detect difference in abstinence rates, as well. We anticipate that the \$0 incentive condition will produce abstinence in 15% of those who contact the TCOS. With n=180/condition, we will have power=.80 to detect at least an 11 percentage point increase in abstinence above the 15% base rate in a 2-tailed test at alpha .05.

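### The primary engagement model leaves out the factors that randomisation is blocked on (clinic, sex, race or minority status); the test is valid but gives up a small, cheaply recovered gain in power

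*Combined protocol and SAP*

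**What the plan says.** Section 6.5 uses tables "to randomize potential enrollees, blocked by clinic, sex, and race, into 1 of 3 engagement incentive conditions". Section 4.1 gives the purpose and names the third factor differently: "Sex and minority status will also be used as blocking factors to limit confounding".

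On the primary aim, section 9.3 says: "The primary analyses will not use covariates. Follow-up analyses will use the patient's home clinic and the patient's TCOS as covariates". TCOS is the tobacco cessation outreach specialist. For the exploratory 6-month abstinence outcome, the main model also has no covariates, secondary models add clinic and TCOS, and then "Gender, race, cigarettes smoked/day will be added as covariates in later analyses". The representativeness aim examines whether "different person factors are significantly related to the various outcomes under the different incentive levels". That relates patient characteristics to outcomes; it is not an adjusted comparison of arms.

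Section 9.4 sizes the trial with an unadjusted comparison of two proportions: "A total of 180 participants per group are needed to have power of .80 with alpha = .05 in a two-tailed test".

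**The concern.** Blocking makes the arms more alike on clinic, sex and race than simple randomisation would. An analysis that omits those factors uses a standard error that takes no credit for the balance. If the factors predict engagement, that standard error is too large, the test rejects a true null less often than 5%, and some power is lost. If they do not predict engagement, nothing is lost.

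The plan treats the three factors as important enough to block on. It then leaves all three out of the primary model and two of them out of every engagement comparison, without giving a reason. Section 9.4 leaves almost no margin above 80% power, so even a small gain that needs no extra recruitment is worth having. Choosing covariates after seeing the data would be open to criticism; naming them now is not.

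**Working it through.** **1. Reproduce the plan's sample size.** Inputs from section 9.4: 15% versus 27%, two-sided alpha .05, power .80. With pooled variance under the null and mean rate .21:

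n = [1.96·√(2·.21·.79) + .8416·√(.15·.85 + .27·.73)]² / .12² = [1.96·.5760 + .8416·.5697]² / .0144 = 179.7, so 180 per arm.

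Power at 180 per arm is .801. The plan's figure holds and matches its covariate-free model.

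**2. Compare the models by simulation.** There were 40,000 trials per cell, with Monte Carlo SE about .002 for power and .001 for type I error. Each trial had 540 patients in 24 strata (6 clinics × sex × binary race), with permuted blocks of 3 or 6 within stratum. Both incentive arms were set at 27%, or all arms at 15% for type I error. The test was a Wald test of one incentive arm against $0. Intercepts were solved so that the marginal rates stayed at the stated values.

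Assumptions not in the documents: block size, equal clinic shares, 50% each sex, 25% minority, and all stratum effects. Cells show blocks of 3 / blocks of 6.

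| Assumed effects on logit scale (clinic SD, sex, race) | Power, no covariates | Power, clinic + sex + race | Gain (points) |
|---|---|---|---|
| None | .806 / .801 | .809 / .804 | 0.3 |
| Weak (.3, .2, .3) | .807 / .803 | .815 / .812 | 0.7–0.9 |
| Modest (.5, .4, .6) | .811 / .809 | .829 / .827 | 1.7–1.8 |
| Strong (.8, .5, .8) | .819 / .814 | .852 / .847 | 3.3 |
| Extreme (1.2, .8, 1.2) | .831 | .890 | about 6 |

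Type I error, covariate-free versus adjusted:
- Modest: .044/.045 versus .050/.051
- Strong: .039/.039 versus .051/.050
- Extreme: .030/.030 versus .051/.049

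With 10% minority and blocks of 6, power was .805 versus .823 (modest) and .816 versus .850 (strong).

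**3. Why power rises although the standard error rises.** In a logistic model the adjusted log odds ratio and its standard error both grow, but the estimate grows more. The ratios are .75/.270 = 2.78 unadjusted, .80/.280 = 2.86 adjusted (modest) and .85/.289 = 2.94 adjusted (strong).

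**4. Cross-checks.**
- Separately coded simulation (6,000 trials per cell, blocks of 3, 15% minority, Monte Carlo SE about 0.5 points): clinic SD .4 with odds ratios of 1.5 for sex and race gave 80.4% to 81.8%. Clinic SD .6 with odds ratios 1.8 and 2.0 gave 81.2% to 83.1%.
- Closed form: power = Φ[(1.96 + .844)/√(1 − R²) − 1.96]. R² of .02, .05 and .08 gives .809, .820 and .832, against .801 with no adjustment.

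**5. The gain in patients.** Putting the blocks-of-3 powers into the step 1 formula:
- Modest: .811 needs 184.8 per arm and .829 needs 193.8, so 3 × 9.0 = about 27 patients.
- Strong: .819 needs 188.7 and .852 needs 206.5, so 3 × 17.8 = about 53 patients.

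**6. What sex and race add.** Adding them to a model that already has clinic gains 0.5 points (modest) to 0.8 points (strong). Most of the benefit comes from clinic.

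**7. Abstinence.** Section 9.4 claims that "we will have power=.80 to detect at least an 11 percentage point increase in abstinence above the 15% base rate". The same formula with 15% versus 26% gives n = [1.96·√(2·.205·.795) + .8416·√(.1275 + .1924)]² / .11² = 210.3, so 211 per arm. Power at 180 is .736. Simulated power with blocks of 6, covariate-free versus adjusted, was .738 versus .741 (no effects), .745 versus .765 (modest) and .747 versus .787 (strong). Adjustment helps but does not restore .80.

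**The case against.** **The plan is consistent and valid as written.** The sample size comes from an unadjusted comparison, the prespecified model matches it, and 80% power is met. This is correct. The patient equivalents in step 5 are surplus above the target, not a shortfall.

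**The size rests on assumed effects.** This also stands. The gain runs from 0.3 points to about 6 across the scenarios and could be negligible. What does not depend on the assumptions is the direction: adjustment cost no power even with no stratum effects.

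**Clinic adjustment is already planned.** True, and clinic carries most of the gain, but only in follow-up models. Sex and race are absent from the engagement comparisons altogether.

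**The simulated setting may differ from the trial.** The simulation treats the 540 as the randomised set and uses rates for two completed calls. Randomisation comes before consent, while several sections describe 540 as recruited. Section 9.3 also words the logistic outcome as any treatment versus none, for which no rate is given. If only consenters were analysed, the blocked balance need not survive and these figures need not apply. This limits the precision of the numbers. It does not undo the point under the intention-to-treat analysis named in section 2.1.

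**Race may have many levels, and data on decliners are restricted.** With an assumed five-level race factor, a level with all or no events arose in 3–37% of simulated trials. The arm test kept its power, but a rule for sparse levels is needed. Section 6.4 says: "Only limited patient and systems data will be shared with the research team documenting which patients were called as standard practice but declined". Section 10.7 describes health-record data as obtained with consent. Keeping blocking values for decliners may therefore need more than analysis-plan wording, although section 9.3 already plans to extract gender and race for the system's smokers.

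**Conclusion.** The concern holds as a minor efficiency point. The covariate-free primary test is valid and meets its planned power. When the blocking factors are prognostic it is conservative: type I error was about .044 under modest and .039 under strong assumed effects. It then forgoes about 1 to 3 points of power under weak-to-strong effects, and essentially nothing if the factors do not matter. The modest-to-strong gain is worth roughly 27 to 50 patients in total. These sizes depend on assumed prognostic strengths, block size, clinic shares and minority proportion, and on analysing all randomised patients.

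The change should be made because it costs little and carries no power penalty, not because the trial is at risk without it. The overstated abstinence power (.736 rather than .80) is a separate error in an exploratory outcome and does not add weight to this point.

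**What to change.** In section 9.3:
- Make the primary logistic model incentive condition + clinic + sex + race/minority status, as main effects coded exactly as in the randomisation tables. Take the p-value from this model.
- Report standardised engagement percentages and risk differences from the same model, because its odds ratio is conditional on the covariates. Do not base the test on the standardised risk difference: its Wald test was slightly liberal in simulation (type I error .051–.055, against .048–.051 for the logistic test).
- Keep the covariate-free model as a sensitivity analysis, and the clinic + TCOS model as planned.
- Use the same three factors in the main 6-month abstinence model.
- State a rule for merging sparse race levels if the tables use more than two.

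Elsewhere, reconcile minority status (section 4.1) with race (section 6.5). State in section 6.4 or 6.5 that the three blocking values are kept for every randomised patient, including those who decline the study, and confirm that the data-sharing permissions cover this.

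The cost is wording, plus keeping three values already needed to apply the randomisation tables and possibly a clarification of permissions for decliners. Sample size and patient contact do not change.

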9.4 Power

This study is powered to detect a 12 percentage point difference in treatment engagement rates (defined as setting a TQD and completing 2 treatment phone counseling contacts) as a function of incentive amount. We believe that this rate is both feasible and of public health significance. We anticipate that the 0 incentive condition will have an engagement rate of about 15%. Since the rate of smoking treatment engagement is generally only about 5-7% in studies where incentives are not used we believe a 15% rate is conservative. We anticipate increased engagement in the control condition, relative to these earlier studies, because we believe it will be increased by TCOS contact and the opportunity to set a quit date on the contact call. We believe that a 12 percentage point increase above the 15% rate (to 27%) would be of public health significance. A total of 180 participants per group are needed to have power of .80 with alpha = .05 in a two-tailed test. This would translate into a study N = 540 with 180/condition for the comparison of each positive incentive condition vs the control condition. We make no a priori prediction about whether the \$100 incentive condition will increase engagement relative to the \$50 condition, but we certainly believe it will increase engagement relative to the 0 incentive condition. . Therefore, we propose an overall N=540.

While engagement is the principal outcome of this research we nevertheless have determined the effect size (increment in percent abstinent) we would need to have adequate power to detect difference in abstinence rates, as well. We anticipate that the \$0 incentive condition will produce abstinence in 15% of those who contact the TCOS. With n=180/condition, we will have power=.80 to detect at least an 11 percentage point increase in abstinence above the 15% base rate in a 2-tailed test at alpha .05.

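### Two primary incentive-versus-control contrasts each carry a two-sided .05 with no testing rule, so the chance of at least one false-positive primary comparison is about 9%, not 5%

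*Combined protocol and SAP*

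**What the plan says.** Section 9.4 (Power) sets the design: "A total of 180 participants per group are needed to have power of .80 with alpha = .05 in a two-tailed test". The assumed control rate is given as "We anticipate that the 0 incentive condition will have an engagement rate of about 15" per cent, and the target effect is that "a 12 percentage point increase above the 15% rate (to 27%) would be of public health significance". The total follows as N = 540, with "180/condition for the comparison of each positive incentive condition vs the control condition". The section makes no prediction for $100 vs $50, but states confidence that $100 will beat $0.

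Section 9.3 (Planned Analysis) describes a logistic regression across the three conditions, "with the 0 incentive condition being the reference condition in the primary analysis". The paragraph of additional exploratory analyses adds that the $100 and $50 conditions will be compared "both with the reference condition and with one another".

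Section 4.1 calls for equal allocation within clinics, "so that roughly 1/3 of all enrollees in a given clinic will be in each of the treatment use incentive conditions".

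Section 3.0 states one hypothesis: modest incentives raise participation and, through it, abstinence. Section 4.1 likewise asks whether financial incentives are effective.

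Neither 9.3 nor 9.4 names a multiplicity adjustment, a testing order, an omnibus test that must be passed first, or a criterion for success on the primary aim. Section 9.3 states no significance level; alpha appears only in 9.4.

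**The concern.** A primary model with $0 as reference yields two coefficients, one per incentive amount. The arms are two amounts of the same intervention, judged on the same outcome against the same 180 controls. Without a decision rule, either significant coefficient could be reported as support for the single hypothesis in Section 3.0, and the .05 in Section 9.4 would then not be the error rate for that hypothesis.

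A split result, with one amount significant and the other not, is also plausible, and the plan does not say how it would be read. Section 10.4 says the results should help identify optimal incentive levels for wider dissemination, so the reading matters.

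**Working it through.** **Inputs.** From 9.4: p0 = .15, p1 = .27, two-sided alpha .05, power .80, n = 180 per arm. From 4.1: allocation 1:1:1. The rate of 21% used below for a weaker arm is an illustrative assumption, midway between 15% and 27%.

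**1. Reproduce the plan's figure.** Pooled-variance formula, no continuity correction, mean rate .21:

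n = [1.960·√(2·.21·.79) + 0.842·√(.15·.85 + .27·.73)]² / .12²

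= [1.960·.576 + 0.842·.570]² / .0144 = (1.129 + 0.480)² / .0144 ≈ 180.

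Power at n = 180 is .801. The stated 180 is therefore reproduced, and it gives the full .05 to one pairwise contrast.

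**2. Correlation of the two contrasts.** Under the null with equal arms, the shared control contributes variance σ²/n to each difference, whose variance is 2σ²/n. The correlation is (σ²/n)/(2σ²/n) = .5.

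**3. Familywise error, each contrast at two-sided .05.** With (Z1, Z2) bivariate normal and correlation .5:

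- Either direction: 1 − P(|Z1| ≤ 1.96, |Z2| ≤ 1.96) = .0907.
- Favouring an incentive only: 1 − P(Z1 ≤ 1.96, Z2 ≤ 1.96) = .0454, against .025 for one contrast.
- Bounds: 1 − .95² = .0975 if the contrasts were independent; .05 + .05 = .10 by Bonferroni.

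Simulation (1,000,000 trials, 15% in all arms, 180 per arm) gives .092 in either direction with pooled z tests and .088 with logistic Wald tests. In the direction favouring incentives it gives .045 and .044.

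**4. Power under rules that hold the familywise error at .05, N = 540.** Simulated with pooled z tests. Each cell shows $100 / $50.

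| True rates $0 / $50 / $100 | Unadjusted | Fixed sequence, $100 first | Hochberg |
|---|---|---|---|
| 15 / 27 / 27 | .81 / .81 | .81 / .69 | .78 / .78 |
| 15 / 21 / 27 | .81 / .32 | .81 / .30 | .73 / .31 |
| 15 / 27 / 15 (only $50 works) | – / .81 | – / about .03 | – / .72 |
| 15 / 15 / 27 (only $100 works) | .81 / – | .81 / – | .72 / – |

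The simulated .81 corresponds to the plan's .80 (.801 by formula). The .03 is .035 if a significant $100 result in either direction opens the second test, and .025 if only a favourable one does.

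**5. Single-step corrections, for comparison.** Bonferroni at .025 each needs 218 per arm (654 in total), or gives .71 power at 180. Dunnett at a nominal .027 each needs 214 per arm (642 in total), or gives .72 power at 180.

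**The case against.** **Per-comparison error control is a recognised position in multi-arm trials.** Section 9.4 sizes each contrast separately, and no passage says that either result alone would count as success. That is fair as far as it goes. However, Sections 3.0 and 4.1 frame one question about incentives, and the arms are amounts of one intervention. If separate claims are intended, the plan should say so.

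**An omnibus test may be intended.** The primary aim concerns the relation between amount and engagement, and the exploratory paragraph of 9.3 describes pairwise comparisons as following the primary analysis. A 2-df test at .05, required before the pairwise tests, would bring the error for the two control contrasts to about 4.2%. The documents neither state nor exclude such a gate. It would also lower power to .76 per contrast at 15/27/27, and to .70 for $100 at 15/21/27, below the .80 in 9.4. This stands as a limit on the point: the 9% describes the plan as sized, with .05 carried over from 9.4.

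**Fixing an order may not suit the trial.** The plan declines to rank $100 against $50, and Sections 3.0 and 7.1 stress modest, affordable amounts, so $50 is a central question. This stands. It is why the sequence is offered below as one option only.

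**Two stronger readings are not supported.**

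- A reader might take 9% as the chance of wrongly claiming that incentives work. About half of the 9% is results in which incentives appear to reduce engagement; the favourable half is about 4.5%.
- A reader might add $100 vs $50 and quote about 12%. Section 9.3 lists that contrast with the exploratory analyses and 9.4 makes no prediction for it, so it is outside the primary error rate.

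**Conclusion.** The point holds as a missing decision rule. With two contrasts at two-sided .05 and none of the controls described above, the chance of at least one false-positive primary comparison is about 9%. In the favourable direction the error rises from 2.5% to about 4.5%. On either scale it is nearly doubled.

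This rests on three assumptions: the two contrasts form one family, the .05 in 9.4 is the level used in 9.3, and no unstated omnibus gate applies. The result depends little on the 15% base rate, since the large-sample calculation uses only the correlation of .5.

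Nothing here shows the sample size to be wrong; 180 per arm is right for one contrast at .05. This is a cheap improvement to the plan, and the design can stay as it is.

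**What to change.** In 9.3 and 9.4, name $100 vs $0 and $50 vs $0 as the primary contrasts, pre-specify one rule that holds their familywise error at two-sided .05, and restate power under that rule. Two options keep N at 540:

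- **Fixed sequence.** Suggested wording: *The first primary test is $100 vs $0 at two-sided .05. If it is significant in favour of the incentive, $50 vs $0 is tested at two-sided .05; otherwise the $50 result is descriptive.* Section 9.4's confidence in the $100 effect supports this order. Power for $100 stays at .80.
- **Hochberg.** Suggested wording: *If both p-values are below .05, both contrasts are declared significant; otherwise a contrast is declared significant only if its p-value is below .025.* This suits a sponsor who does not want to rank the amounts.

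If an omnibus gate was intended, write it down and restate power accordingly. Under any rule, $100 vs $50 stays exploratory. State also how a split result will be reported.

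**Cost.** Wording only, with no change to N, data collection or conduct. Power for at least one contrast falls below the stated .80. Under the fixed sequence there is no confirmatory $50 claim if $100 fails, so $50 power drops to about .03 if only $50 works. Hochberg avoids that, at the price of .72 power when only one amount works.
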